ii. Visit 2: 6-month BP Measurement Assessment and Medication Use

A follow-up visit will be conducted by study staff in all three arms approximately 6 months after enrollment (allowing for a one-month window). BP measurements will be conducted by study nurses independently from the CHW program using standardized Omron BP cuffs. Three measurements will be taken from the seated position with five minutes between each measure [14]. At the 6-month visit we will additionally collect data on medication regimen changes and adherence (Table 1).

iii. Visit 3: 12-month BP Measurement Assessment and Evaluation of BP Device Function

A final home-based study visit in all three arms will be conducted 12 months after enrollment (allowing for a one-month window period). BP measurements will be conducted using standardized Omron BP cuffs by study staff, independently of CHW

interactions with study participants. Three measurements will be taken from the seated position with five minutes between each measure [14]. We will also collect data on self-reported medication regimen changes, adherence, quality of life, and resource use (Table 1).

iv. Extension phase and additional study visits: 18 and 24-month BP Measurement Assessment and Evaluation of BP Device Function

At the conclusion of the 12-month study visit, individuals in the community-based blood pressure arms will be invited to consent for a continuation phase of the project to assess the longer-term impacts of the project. The extension phase will coincide with the period when initial participants complete their 12-month visit to the conclusion of all participants completing 12 month visits. Participants who agree to this continuation will remain in the community-based program, retain their BP cuffs, and be visited by CBPMs with their blood pressure treatment monitored by clinic nurses. For those who consent to the extension phase, study team members will continue home-based visits every 6 months to monitor blood pressure readings and complete questionnaires for study purposes.

v. Missing and Late Appointments

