We will summarize participant sociodemographic and clinical characteristics at baseline in all three arms. We will use linear regression to estimate the difference between arms, and its 95% confidence interval (CI), in systolic blood pressure at 6 months, adjusted for baseline systolic BP. We will use logistic regression to estimate odds ratios (OR) and 95% CIs for the impact of the intervention on the proportion of participants who achieve blood pressure control (<140/90) at 6 months.

Characteristics of individuals who are lost to follow-up will be tabulated by study arm. Since study nurses will visit all participants at home to measure blood pressure at 6 and 12 months, we do not expect there to be differential loss to follow-up between arms. In the primary analyses, participants with missing data at 6 months will be excluded. In sensitivity analyses, those with missing measurements will be considered to have no change in systolic BP and uncontrolled BP. Missing values may also be imputed using multiple imputation.

In pre-planned secondary analyses, we will fit regression models stratified by sex (to assess for sex as a biologic variable), age strata, socioeconomic status and baseline co-morbidities (i.e. obesity and HIV) to determine sub-group effect sizes and test the significance of an interaction term between sub-groups and the intervention to assess for effect modification.

A detailed statistical analysis plan will be prepared before the data are examined by treatment arm.

M. Risks, Protection from Risks and Benefits to Study Participation in Aim 2

a. Risks and Protections

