Sustainability	
 - Number of participants counseled in lifestyle modification and medication adherence at home by CBPMs. - Number of clinics adopting use and distribution of BP cuffs for HBPM. - Proportion of clinics sustaining use and distribution of BP cuffs for HBPM at 12 months, among those who distributed BP cuffs at the start of the study. - Proportion of participants retained in hypertension care at 12 months, among enrolled study participants. - Absolute change in systolic blood pressure (SBP) between 6 and 12 months after enrollment, among enrolled study participants. - Proportion of participants retained in hypertension care at 12 months, among enrolled study participants. - Absolute change in systolic blood pressure (SBP) between 6 and 12 months after enrollment, among all study participants. 	
 - CBPM study records. - Study check lists. - Study check lists. - Participant study records. - CDS records - Participant study records. - CDS records.

C. Data Sources

a. (Aim 3a) Fidelity, Sustainability, and Acceptability

Both the fidelity and the sustainability of the intervention will be assessed using data obtained through review of study check lists, the participant study records (including prescriptions), CDS records, CBPM study records, outreach team leader supervision records, and coordination meeting minutes.

Key informant and individual interviews will assess overall acceptability and experience of the intervention.

b. (Aim 3b) Cost-effectiveness

Cost data will be obtained from trial participant interviews, KZN DoH unit prices, and analysis of intervention delivery.

The trial will provide individual level outcome data on SBP and blood pressure control 6 and 12 months. The PREDICT model will use these data to predict long term effects of the interventions on quality adjusted life years (QALYs)

D. Recruitment

a. (Aim 3a) Fidelity, Sustainability, and Acceptability

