Persons who participated in Aim 1 activities and who will participate in Aim 3 activities, will be re-consented regardless of whether they provided verbal or written consent in Aim 1. Consenting procedures for Aim 3 will be identical to those described in Aim 1.

- b. (Aim 3b) Cost-effectiveness
This will be included in the consent to participate in the trial.

H. Data Collection

- a. (Aim 3a) Fidelity, Sustainability, and Acceptability
Data on fidelity outcomes will be obtained from study checklists and data collected with the electronic hypertension management tool in the intervention arms at 6, 12, 18 and 24 months. Sustainability measures, including changes in systolic blood pressure, will be collected using the same sources at 12 months in the intervention arms. In the standard of care arm changes in systolic blood pressure at 12 months and medication use will be obtained through participant chart reviews. All data will be combined into a database for analyses and all personal identifiers will be removed prior to analysis. Interviewers will use guides with open-ended questions to collect qualitative data on the overall acceptability of the intervention.
- b. (Aim 3b) Cost-effectiveness
Resource allocation assessments in all three study arms will be conducted at 6 and 12 months after the start of the trial using a time and motion study over five clinic days, along with medical records reviews and participant exit interviews. Using these measurements, the public-sector unit costs for managing hypertension will be calculated, including human resources, diagnostics and supplies, therapeutics, and home blood pressure monitors. Costs will be collected from relevant sources, including clinic sites, the South African

Department of Health, and published reports. A societal perspective will be applied to data collection and analysis.

I. Analysis

a. (Aim 3a) Fidelity, Sustainability, and Acceptability

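### Protocol VI.H.a takes the Aim 3a sustainability SBP change from different records in the intervention and SOC arms, and the protocol is inconsistent about the source

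*Protocol*

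**What the plan says.** Protocol VI.H.a (Aim 3a, Data Collection) first gives the source for fidelity: "Data on fidelity outcomes will be obtained from study checklists and data collected with the electronic hypertension management tool in the intervention arms". It then extends that source to sustainability: "Sustainability measures, including changes in systolic blood pressure, will be collected using the same sources at 12 months in the intervention arms". For the control arm it names another: "In the standard of care arm changes in systolic blood pressure at 12 months and medication use will be obtained through participant chart reviews".

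Table 4 in VI.B supplies the definition of the outcome: "Absolute change in systolic blood pressure (SBP) between 6 and 12 months after enrollment, among all study participants". Its source column lists participant study records and CDS records. Section VI.C.a lists those two and several others as sources for fidelity and sustainability, but not clinic charts. Section VI.A.a places sustainability measurement at the 12-, 18- and 24-month visits.

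Aim 2 plans blood pressure readings that do not depend on care. Under V.G.b.ii, "A follow-up visit will be conducted by study staff in all three arms approximately 6 months after enrollment"; under V.G.b.iii, "A final home-based study visit in all three arms will be conducted 12 months after enrollment". Both visits use three seated readings on standardised Omron cuffs, taken independently of the community health worker program. Section V.L relies on this: "Since study nurses will visit all participants at home to measure blood pressure at 6 and 12 months". Section V.A and SAP section 5 agree. SAP section 7 takes the mean of the second and third readings as the visit value. SAP section 2 leaves sustainability to a separate analysis plan, which is not among the documents.

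**The concern.** An outcome defined over all study participants should be measured in the same way in every arm. Followed as written, VI.H.a would draw SBP from records kept for care, and those records differ by randomised arm. Any by-arm reading of the sustainability outcome would then mix a difference between arms with a difference between sources. Comparable readings are already scheduled in every arm, so this is avoidable.

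At stake is a second version of the 6-to-12-month SBP result, reported as the sustainability finding and not comparable across arms, beside results taken from the study visits.

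**Working it through.** The documents give no figure to reproduce, so the check sets the statements side by side.

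**1. What each arm's care records contain.**

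| Arm | Source under VI.H.a | Readings behind it |
|---|---|---|
| CBPM | Checklists and electronic tool | Daily home readings on an Omron cuff, collected at CBPM visits every 2-4 weeks (V.G.a.ii) |
| eCBPM+ | Checklists and electronic tool | Daily home readings on a cellular cuff, uploaded automatically (V.G.a.iii) |
| SOC | Chart review | If the chart is the clinic record: clinic readings on routine clinic equipment, at visits that become 6-monthly once blood pressure is controlled (V.G.a.i) |

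Section V.H.a.ii says that the decision support system receives blood pressure information every two to four weeks, and only in the two intervention arms. CDS records therefore cannot supply SOC values.

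Reading chart as clinic record is an inference. It rests on two places: V.G.b.i separates review of clinic records from the nurses' measurements, and Table 1 reserves chart review for medication and laboratory history, with blood pressure in its own row.

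**2. What the protocol says elsewhere about the source.**

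- VI.A.a: sustainability at the 12-, 18- and 24-month visits, fidelity at 6 and 12 months.
- VI.H.a: sustainability at 12 months, fidelity at 6, 12, 18 and 24 months.
- VI.C.a and Table 4: participant study records and CDS records among the sources. The pairing of outcomes with sources in Table 4 is uncertain in the extracted text.
- VI.C.b (Aim 3b): "The trial will provide individual level outcome data on SBP and blood pressure control 6 and 12 months". Aim 3b thus uses the trial's own SBP data.

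These do not describe one source or one schedule.

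**3. Effect of a source offset.** Let x6 and x12 be a participant's study-visit values, and d a constant offset of the care record from the study reading.

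- Care record at both times: (x12 + d) - (x6 + d) = x12 - x6. Artefact 0.
- Study reading at 6 months, care record at 12: (x12 + d) - x6 = (x12 - x6) + d. Artefact d.
- If both arms mix sources in this way, with offsets dI (intervention) and dS (SOC), the between-arm contrast moves by dI - dS.
- Study-visit readings at both times in all arms: no offset enters.

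VI.H.a names a source only at 12 months, so the text does not say which case applies, and no document gives d. Purely as an assumption, d between 0 and 5 mmHg would move a mixed-source arm's change by 0 to 5 mmHg. The documents favour no value in that range, nor a sign.

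**4. Whether the SAP already supplies the comparison.** The section 10 mixed model uses SBP at the 6- and 12-month visits, with arm, visit and their interaction. With month 6 as reference, the interaction coefficient is the between-arm difference in 6-to-12-month change. If the interaction is not significant at p < 0.10 it is dropped, and the model then gives one overall effect per intervention and sets that difference to zero. SAP 9.1 tabulates change from baseline by arm, not change from 6 to 12 months.

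**The case against.** The strongest reply is that nothing here is a flat contradiction. Aim 2 says which readings study staff take, VI.H.a says which records Aim 3a uses, and both can be carried out. Section VI.A.a ties sustainability to the 12-month visit, where the Omron readings are taken in all arms. Participant study records, listed in VI.C.a and Table 4, could hold those readings. SAP section 5 also says that other data from the follow-up visits serve estimates of sustainability, although that list does not name blood pressure. The separate plan may settle the matter.

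Much of this stands, and it is why the point is minor. It does not remove the point: VI.H.a names other sources explicitly, by arm, and the more favourable passages show that the sections need to be reconciled.

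A reader might infer more than the documents support:

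- That SOC participants have no standardised 12-month reading. Section V.G.b.iii plans one in all three arms.
- That an SOC chart value exists only if the participant attends the clinic. Section V.G.a.i also allows monitoring by CBPMs in this arm, without saying whether it yields blood pressure readings.
- That a biased comparison of arms is planned. Section VI.I.a says only that statistics will be generated. VI.H.a combines all data in one database but does not specify pooling the arms on SBP.
- That section 10 of the SAP already guarantees a valid 6-to-12-month comparison. It does so only if the interaction is retained.

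**Conclusion.** The point holds as a minor inconsistency. As written, VI.H.a gives the Aim 3a SBP change a source that differs by randomised arm, and the Aim 3a sections do not agree on the source or the schedule. That device, setting and timing also differ is probable. For SOC it rests on reading chart as the clinic record.

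The size and direction of any bias cannot be determined. A constant offset contributes nothing if each arm keeps one source at both times, and its full value if the source changes between them.

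The reach is this one outcome. The 6-month primary and secondary outcomes and the 12-month SAP analyses rest on study-visit readings and are unaffected. It would be wrong to conclude that the trial's effectiveness results are compromised. The judgement is on the protocol text, since the separate sustainability plan was not available.

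**What to change.** In Protocol VI.H.a, Table 4 and the separate sustainability plan, name the month-6 and month-12 study-visit readings, each the mean of the second and third measurements as in SAP section 7, as the source of the 6-to-12-month SBP change in all three arms. Reconcile VI.A.a, VI.C.a, Table 4 and VI.H.a on source and on which visits serve fidelity and which serve sustainability. Keep chart and CDS data for medication use and fidelity measures. If by-arm results for this outcome are to be shown, the separate plan should say how the 6-to-12-month difference will be estimated if the section 10 interaction is dropped.

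The cost is wording only. The measurements are already scheduled in every arm at both visits, so no new data are needed.

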- ii. Some participants might gain a personal sense of pride from knowing they are contributing to development of a system that intends to improve hypertension care in their community, or for the opportunity to contribute to its design.
- iii. If one of the interventions is ultimately successful, this study might provide a benefit to the community by helping to guide development of an improvement system of hypertension care.
- iv. A financial incentive of R50 of airtime (telephonic), R50 in cash (in-person), or a R50 food voucher will be provided to participants for their participation in discussion groups and interviews, subject to COVID-19 restrictions in place.

[figure not shown]
V. AIM 2: IMPLEMENTATION CLINICAL TRIAL

Determine the effectiveness of community-based, technology-supported interventions to reduce systolic blood pressure and increase blood pressure control among individuals with uncontrolled hypertension in rural South Africa.

A. Aim 2 Overview

This is randomized clinical trial intended to identify the optimal strategy of blood pressure management in rural South Africa. Participants will be randomized into one of three arms of hypertension care: 1) clinic-based standard of care model (SOC); 2) community blood pressure monitor-based blood pressure monitoring model (CBPM); 3) an enhanced community blood pressure monitor-based model with mobile health blood pressure monitoring (eCBPM+). (Figure 1). Eligible participants will be recruited from prior community-based hypertension screening programs, CBPM-led hypertension screening activities, and/or from trial clinics where they are accessing care. Consenting participants will be randomized to one of the three study arms. Independent of clinical care, all participants will be seen at enrollment, at 6 months, and at 12 months for BP monitoring and data collection by study nurses for outcome assessments.

Figure 1. Study Schema

The primary effectiveness outcome will be assessed in an intention-to-treat analysis and defined as the change in systolic blood pressure (SBP) 6 months after enrollment. The secondary effectiveness outcome will be the proportion of participants with controlled blood pressure, as defined by an SBP <140 mmHg and a diastolic BP (DBP) <90 mmHg 6 months after enrollment.

B. Eligible Study Population

Residents living in the catchment area of publicly operated rural primary care clinics in the Umkhanyakude District in northern KwaZulu Natal.

C. Eligibility Criteria

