Participants in the (eCBPM+) Arm will also be given a home BP cuff, but in this case these cuffs will include cellular network capability (Blipcare model), such that BP data can be directly transmitted to the electronic platform to allow nursing supervisor review. Similar to the standard CBPM arm, they will also be given training on its operation and assigned a CHW from the study team. Participants in this arm will be instructed to take daily BP measurements, which will be automatically uploaded onto the server to be made available by the nurse supervisors. CBPMs will return to participant homes every 2-4 weeks to ensure functionality of the devices and transmission, collect BP measurements if the system is not functional, assess for symptoms, and discuss treatment adherence and lifestyle recommendations. Nursing supervisors at the clinic will use the remotely collected BP data to initiate and tailor medications guided by the same standardized clinical decision support (CDS) algorithm, based on SA DoH hypertension control guidelines. Treatment decisions will be made by the nursing supervisors. Participants will either obtain medication(s) at the pharmacy or, as possible, have them delivered by a CBPM. As per the SOC arm, medications used will include those on the South African Essential Drug list and which are available in the clinic pharmacy (include hydrochlorothiazide, enalapril, amlodipine and atenolol). Participants who achieve optimal blood pressure control may have visits spaced out if recommended by the nursing supervisor.

Figure 4. Intervention 2: eCBPM+ Care Model.

b. Study Visit Schedule

i. Visit 1: Enrollment

At Study Visit 1, participants will complete the baseline questionnaire to collect sociodemographic, clinical and treatment history, self-reported medication adherence, quality of life, and resource allocation data (Table 1). Enrollment BP measurements will be collected by study nurses (independently from the CHW program) using standard BP measuring devices (OMRON model). Three measurements will be taken from the seated position with five minutes between each measure [14]. As described during the recruitment phase, all participants will receive a point of care (POC) creatinine (Abbott/Piccolo Xpress) to determine both eligibility and to guide BP regimen selection. Study staff will also review participant clinic records to collect data on clinic treatment history and blood pressure measurements in the past.

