Cost-effectiveness of the intervention compared to standard of care in blood pressure management, will be calculated as incremental costs for absolute changes in blood pressure (costs/mmHg) and incremental costs per extra participant with controlled blood pressure. The Harvard CVD PREDICT microsimulation model for cost-effectiveness and changes in CVD-related health outcomes will be used to conduct this analysis. The cost-effectiveness will be calculated across the entire intervention, as well as separately by each of the study arms.

B. Study Outcomes

a. (Aim 3a) Fidelity, Sustainability, and Acceptability

Study outcomes measuring acceptability, fidelity, and sustainability of the intervention are summarized below in **Table 4**.

c. (Aim 3b) Cost-effectiveness

- Costs to participants of health care including (where applicable) the interventions
- SBP reduction and blood pressure control resulting from the interventions
- Quality adjusted life years (QALYs)
- Incremental cost-effectiveness ratios (ICERs), that is, incremental cost per mmHg SBP reduction, per extra participant with controlled blood pressure, and per QALY gained as effects of the interventions

Table 4. Summary of acceptability, fidelity, and sustainability outcome measures for Aim 3a

Acceptability	
 - Participant and provider perception of the intervention and clinical decision support tools. 	
 - Key informants interviews. - Individual interviews.
Fidelity	
 - Proportion of successful and failed BP data transmission events, among all transmitted BP data events. - Proportion of CDS-recommended treatment changes initiated by nurse/CBPM, among all CDS-recommended treatment changes. - Number of BP cuffs distributed to participants in 2 intervention arms. - Number of BP readings manually recorded by intervention participants. - Number of CBPMs trained on HBPM and data tool input/management. - Number of participants with treatment initiation during study period. - Number of BP cuff training sessions provided to participants at home by CBPMs. - Number/frequency of CBPM home visits conducted versus planned 	
 - Study check lists. - CDS records. - Study check lists. - Participant study records. - Outreach team leader supervision records. - CBPM study records. - CBPM study records

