Quantitative data will be analyzed using Stata Statistical Software (Release 17. College Station, TX) and statistics for fidelity and sustainability outcomes will be generated. Qualitative data analysis will be performed using similar methods as in Aim 1. The key informants and individual interviews will be collected in isiZulu, then transcribed, and translated in English by a team of social science research assistants. A data-led coding framework will be developed, based on themes, which emerge from the data. The research assistants involved in collecting the data will work with other social science team members to agree on the coding framework and performing coding of the data. Thematic summaries will be prepared using the data and a process of building consensus among the whole study team. These summaries will form the building blocks for reporting the findings. Organization of data on the acceptability of the intervention will again be organized into component constructs using the Theoretical Framework for Acceptability, as described in Aim 1.

b. (3b) Cost and Cost-effectiveness

Cost-effectiveness of the intervention compared to standard of care in blood pressure management, will be calculated as incremental costs for absolute differences in blood pressure (costs/mmHg) and incremental costs per extra participant with controlled blood pressure. This analysis will be performed using the Harvard CVD PREDICT model [15] for cost-effectiveness and changes in CVD-related health outcomes. The model will be used to assess the cost-effectiveness of the intervention and to model the impact on the observed change in systolic blood pressure on future CVD events. We will also use the model to translate the intervention effectiveness established during the trial into quality adjusted life years (QALY) and applying assumptions about effects of SBP reductions on survival, quality of life, and complications, based on the extant literature and confirmed locally as part of this trial.

The cost-effectiveness will be calculated across the entire intervention, as well as separately by each of the study arms and expressed in incremental cost-effectiveness ratios (ICERs) and quality adjusted life years (QALYs).

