9.1 Primary objective

The primary objective of the trial is to examine the effect of the interventions on the change from baseline in systolic blood pressure 6 months after enrolment. The mean

and SD systolic blood pressure, and the mean and SD change from baseline, at the 6 and 12 month visits will be summarised by treatment arm.

Linear regression will be used to estimate the mean difference, and its 95% confidence interval (CI), between each intervention and SOC (i.e. CBPM vs SOC and eCBPM+ vs. SOC) in the change from baseline at 6 months. The response variable will be systolic blood pressure at 6 months; the model will include treatment arm, clinic, active use of hypertension medication and baseline systolic blood pressure.

In secondary exploratory analyses, we will adjust for baseline values of age, sex, body mass index (BMI), smoking status and HIV. In separate models, we will fit an interaction term between the treatment arm and sub-groups of interest (e.g. sex, age group, co-morbidities) to examine sub-group effect sizes and potential effect modification.

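### Aim 3b plans no eCBPM+ versus CBPM step or dominance check, so ratios against standard of care could make eCBPM+ look good value when its increment over CBPM is not

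*Protocol*

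**What the plan says.** Protocol VI.A.b (Aim 3b methods) and VI.I.b (Aim 3b analysis) use almost the same wording. Each sets the comparator first: "Cost-effectiveness of the intervention compared to standard of care in blood pressure management, will be calculated as incremental costs". Each then says what will be produced: "The cost-effectiveness will be calculated across the entire intervention, as well as separately by each of the study arms". VI.I.b adds that results are expressed as ICERs and QALYs. The Aim 3b outcomes in VI.B give the units: "incremental cost per mmHg SBP reduction, per extra participant with controlled blood pressure, and per QALY gained as effects of the interventions".

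VI.I.b also plans a probabilistic sensitivity analysis and cites good-practice guidance for the cost-utility model, but states no rule for which options are compared with which. On the effectiveness side, SAP 9.1 estimates differences "between each intervention and SOC (i.e. CBPM vs SOC and eCBPM+ vs. SOC"). SAP section 2 leaves cost-effectiveness to a separate analysis plan, which is not among the documents.

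The Aim 2 overview (Protocol V.A) describes the trial as "intended to identify the optimal strategy of blood pressure management in rural South Africa", and SAP section 1 states the same aim.

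**The concern.** SOC, CBPM and eCBPM+ are alternatives: a given patient is managed under one of them. When several alternatives compete, the ratio that informs the choice compares each option with the next less costly one still in contention, after removing options that are dominated (no more effective and more costly) or extendedly dominated (beaten by a mix of two others). A ratio against SOC answers a narrower question, namely whether the option beats doing nothing new.

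The distinction matters here because the two interventions are close relatives. Both use home cuffs, nurse-led treatment decisions and the same decision-support algorithm. The eCBPM+ arm keeps the home visits at the interval used in CBPM: "CBPMs will return to participant homes every 2-4 weeks to ensure functionality of the devices and transmission". What mainly changes is the cellular cuff and automatic upload. A policy maker would therefore want to know whether that step is worth its cost. None of the planned ratios, as naturally read, answers this, and a pooled figure averages over it.

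The risk is that a report shows eCBPM+ under a willingness-to-pay threshold against SOC, and the reader concludes that it should be bought, when CBPM gives nearly all the benefit for less.

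**Working it through.** **The plan's own figures.** Aim 3b states no cost, ratio or threshold, so there is nothing economic to reproduce. The sample size can be reproduced, and it shows how precisely the trial can separate eCBPM+ from CBPM. Inputs (Protocol V.J.a, SAP section 6): difference 5 mmHg, SD 19, correlation 0.5, alpha 2.5% (taken as two-sided), power 80%, 20% loss.

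- Baseline-adjusted variance: 19² × (1 − 0.5²) = 270.75.
- n per arm = 2 × (2.241 + 0.842)² × 270.75 / 5² ≈ 206.
- Enrolled per arm: 206 / 0.80 = 257.5, so 258, as stated.

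**Illustration in cost units (assumed).** Against SOC, take CBPM at +60 for 5 mmHg and eCBPM+ at +120 for 6 mmHg.

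- CBPM vs SOC: 60 / 5 = 12 per mmHg.
- eCBPM+ vs SOC: 120 / 6 = 20.
- Pooled, equal arms: 90 / 5.5 = 16.4.
- eCBPM+ vs CBPM: (120 − 60) / (6 − 5) = 60.

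The pattern is structural. When eCBPM+ costs more and works better, its ratio against SOC is an effect-weighted average of the two steps: (5/6) × 12 + (1/6) × 60 = 20. It understates the cost of the second step whenever that step is less efficient than the first.

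If both arms lower SBP by 5 mmHg, eCBPM+ vs SOC is 120 / 5 = 24, yet eCBPM+ costs more for the same effect and is dominated.

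**Varying the inputs (assumed).** Express cost in multiples of the willingness to pay per mmHg, so the threshold is 1. Hold CBPM at cost 3 and 5 mmHg (ratio 0.60, net benefit 5 − 3 = 2.0).

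| Case | eCBPM+ effect, cost | vs SOC | Pooled | vs CBPM | eCBPM+ net benefit |
|---|---|---|---|---|---|
| a | 5.5, 4.4 | 0.80 | 0.70 | 1.4 / 0.5 = 2.8 | 1.1 |
| b | 4.5, 4.0 | 0.89 | 0.74 | dominated | 0.5 |
| c | 7.0, 4.0 | 0.57 | 0.58 | 1.0 / 2.0 = 0.50 | 3.0 |

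In (a) and (b) the SOC and pooled ratios both pass the threshold although CBPM has the higher net benefit. In (c) there is no conflict: eCBPM+ is best on every measure. CBPM is then extendedly dominated (0.50 is below 0.60), so the ratio of eCBPM+ against SOC is the right one. Over eCBPM+ effects of 4.5 to 7.0 mmHg and costs of 3.5 to 5.0, the step from CBPM ran from 0.25 to 4.0, or eCBPM+ was dominated.

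**Precision of the missing contrast.** From the plan's inputs, the SE of the eCBPM+ minus CBPM difference in SBP is √270.75 × √(2/206) = 1.62 mmHg, a 95% half-width of 3.2 mmHg. If eCBPM+ were truly 1 mmHg better, it would still look worse than CBPM in Φ(−1/1.62), about 27% of trials; at 0.5 mmHg better, about 38%. A point ratio for this step would be fragile, so it needs to be reported with joint uncertainty in cost and effect.

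**The case against.** The strongest reply is that the documents are silent on this comparison and do not fix a wrong rule.

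- The detailed economic plan announced in SAP section 2 was not supplied and may already set out a three-way incremental analysis. This stands, and it limits the point to what the protocol states.
- The sentence on arms names no comparator, and SOC is itself a study arm, so nothing literally confines the ratios to SOC. The entire-intervention figure is also undefined. Both are fair. A reader might infer that the protocol prescribes a pooled ratio and forbids any other contrast, but the text does not go that far. Pooling and comparison with SOC are the natural readings, since SOC is the only comparator named in either section.
- The guidance cited in VI.I.b might require a full incremental analysis. Its content cannot be checked from the documents, so it counts neither for nor against the point.
- The direction of cost is not established. A cellular cuff may cost more, but automatic upload replaces manual collection and entry of readings. This stands.
- A mixed roll-out is conceivable, because the protocol treats cell coverage as a readiness question and provides manual collection when transmission fails. So an overall figure is not meaningless, though nothing suggests that an equal mix is the option under consideration.
- The policy benefit described in VI.J.b asks whether the interventions are a good use of resources, which ratios against SOC do address. The trial's overall aim of finding the optimal strategy is not met by them.
- Readers could derive the missing step if costs and effects are reported by arm. They could not derive its joint uncertainty.

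**Conclusion.** The point holds as a cheap improvement. As naturally read, Aim 3b reports a pooled ratio and each intervention against SOC, and states no increment between the two interventions and no dominance check, while the trial sets out to choose among three strategies. If eCBPM+ costs more than CBPM, those ratios can favour it when its step over CBPM is poor value (20 against SOC, 60 against CBPM) or dominated (24 against SOC).

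The sizes rest wholly on assumed costs and effects; the documents supply neither costs nor a threshold. Three stronger conclusions are tempting and not supported: that the analysis will mislead (case c shows no conflict), that eCBPM+ is known to be the dearer arm, and that the unseen economic plan repeats the gap. Trial data, randomisation and the primary blood pressure result are unaffected.

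**What to change.** In Protocol VI.A.b and VI.I.b, and in the separate economic plan:

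1. Make the primary economic analysis fully incremental. Order SOC, CBPM and eCBPM+ by cost, remove dominated and extendedly dominated options, and report each ICER against the next remaining option. This works whichever intervention proves dearer.
2. Use the planned probabilistic sensitivity analysis to report joint uncertainty in cost and effect, and the probability that each of the three strategies is optimal across a range of thresholds.
3. Keep ratios against SOC as secondary results.
4. Drop the entire-intervention ratio, or define it and label it descriptive.

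If the economic plan already does this, aligning the two protocol sections with it is enough. The cost is wording and a little more analysis. Resource use is already to be assessed in all three arms (VI.H.b) and all participants enter the cost analysis (VI.F.b), so no new data or model is needed.
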